4.2.2 Inclusion and Exclusion Criteria for Pediatric Participants

4.2.2.1 Inclusion and Exclusion Criteria for Pediatric Stage 1

4.2.2.1.1 Inclusion Criteria for Pediatric Stage 1

Individuals who meet all of the following criteria are eligible for enrollment randomization/allocation as participants in Pediatric Stage 1:

1. Individuals 2-17 years of age that meet classification criteria for SLE, JIA, POMS, or JDM. Note: Juvenile idiopathic arthritis includes the following conditions: polyarticular JIA (both RF + and -), oligoarticular persistent and oligoarticular extended JIA, psoriatic arthritis, and enthesitis related JIA.

- a. Participants must meet the 2017 EULAR/ACR classification criteria for adult and juvenile idiopathic inflammatory myopathies and their major subgroups [8], the International League of Associations for Rheumatology (ILAR) classification for JIA [4], the 2017 McDonald [6] criteria for MS, or the Bohan and Peter criteria or the 2017 EULAR/ACR classification criteria for JDM.
- b. If a participant has been diagnosed with more than one autoimmune disease, the participant will be assessed based on the disease that is selected for study entry.

2. Parents/guardians of all pediatric participants and participants ages 14 – 17 must be willing and able to sign informed consent. Participants ages 7-13 must be willing and able to sign assent.
3. Documented EUA-authorized or FDA-approved COVID-19 vaccine doses (CDC card or documentation in medical records) that was completed at least 4 weeks prior and no more than 52 weeks prior to the Screening visit.
4. Negative or suboptimal serologic response to initial EUA-authorized or FDA-approved COVID-19 vaccine doses, defined as an Elecsys® Anti-SARS-CoV-2 S result ≤ 200 U/mL, or a low immune response, defined as an Elecsys® Anti-SARS-CoV-2 S (RBD) result of ≤ 2500 U/mL, within 4 weeks of the Stage 1 Baseline/Week 0 visit.
 - a. Initial COVID-19 vaccine regimen is defined as:
 - i. Pfizer-BioNTech COVID-19 Vaccine (2 through 4 years of age): 3 age-appropriate doses.
 - ii. Pfizer-BioNTech COVID-19 Vaccine (5 through 17 years of age): 2 age-appropriate doses.
 - iii. Moderna COVID-19 Vaccine (2 through 17 years of age): 2 age-appropriate doses.
5. Must be currently taking one of the following IS medications with or without additional disease-related medications: MMF (minimum of 250 mg per day)/MPA (minimum of 360 mg per day), MTX (minimum of 5 mg per week), or B cell depleting agents within the past 18 months (such as rituximab, ocrelizumab, or ofatumumab).
 - a. If taking MMF/MPA or MTX, the participant must have initiated therapy at least 8 weeks prior to randomization and be taking the same medications (regardless of dose) as at the time of the initial COVID-19 vaccine regimen. Note: Participants who withheld their IS medications around their initial vaccinations are eligible to participate.
 - b. If enrolling in the BCDT cohort, participant must have received an anti-CD20 or an anti-CD19 BCDT in the past 18 months.
6. No changes in background IS medications, including MMF/MPA or MTX, in the 8 weeks prior to Screening, excluding the following:
 - a. HCQ,
 - b. Intraarticular steroids,
 - c. The addition of prednisone at <0.15 mg/kg/dose per day or prednisone at any dose when given for ≤ 3 days, and
 - d. Corticosteroid bursts for non-autoimmune disease-related conditions, such as asthma or COPD, are permitted.

4.2.2.1.2 Exclusion Criteria for Pediatric Stage 1

Individuals who meet any of these criteria are not eligible for randomization/allocation as participants in Pediatric Stage 1:

1. Inability or unwillingness of a participant to give assent or consent; or of a parent/guardian to give written informed consent, or of either to comply with study protocol.
2. History of severe allergic reaction to the initial COVID-19 vaccine regimen, or any component of any of the COVID-19 vaccines, or to PEG.

3. New diagnosis of malignancy that will require chemotherapy or immunotherapy, or ongoing treatment for a malignancy with chemotherapy or immunotherapy.
4. Active disease (per the Investigator's decision) resulting in inability to hold the IS therapy in the MMF/MPA or MTX arms of the study.
 - a. The potential impact of temporarily holding medication for participants with a recent mild disease flare within 4 weeks should be carefully considered.
5. Active disease during the Screening period resulting in:
 - a. an increase/addition of any IS medications, or
 - b. a suggestion of MS relapse per the investigator
6. Recent or current SARS-CoV-2 infection defined as:
 - a. Documented SARS-CoV-2 infection in the past 30 days (from the day the participant is diagnosed by positive test to Screening).
 - b. Positive result on a molecular COVID-19 test at Screening.
7. Receipt of a COVID-19 vaccine booster prior to Screening.
8. Inflammatory myocarditis/pericarditis within 6 weeks of any COVID-19 vaccine doses.
9. Participants with active, ongoing chronic infections.

Note: Participants are permitted to be on chronic prophylactic antimicrobial therapy.

10. Participants with common variable immunodeficiency disease, as well as any participants currently receiving immune globulin replacement therapy.

Note: Participants on IVIG therapeutically may enter the study provided they have sufficiently quiet disease that they can withhold their IVIG from 8 weeks prior to the Screening visit through 4 weeks after vaccination.

11. Participants who received licensed or investigational monoclonal antibodies or plasma products directed against SARS-CoV-2 within 30 days of Screening.
12. Participants who have received any live vaccines within 2 months of the anticipated study vaccine dose or who will have need of a live vaccine at any time during the study.
13. Currently pregnant or breastfeeding (postmenarchal females must have a negative urine pregnancy test at Screening)
14. Hemoglobin (Hgb) <8.0 g/dL (80 g/L)
15. Past or current medical problems or findings from physical examination or laboratory testing that are not listed above, which, in the opinion of the investigator, may pose additional risks from participation in the study, may interfere with the participant's ability to comply with study requirements or that may impact the quality or interpretation of the data obtained from the study.
16. Other investigational chemical agent within 30 days or other investigational biologic agent within 8 weeks or 5 half-lives (whichever is longer) of Screening.
17. Concurrent treatment with cyclophosphamide.
18. Participants currently on any type of dialysis, or who have received a solid organ transplant.
19. Prisoners or participants who are compulsorily detained (involuntarily incarcerated) for treatment of either a psychiatric or physical (e.g., infectious disease) illness must not be allowed to participant in this study.
20. Taking both MMF/MPA and MTX.

21. Other investigational BCDT as part of a clinical trial within 18 months of Screening, unless drug assignment is known and the participant received an anti-CD20 or CD19 drug.
22. Participants with active systemic infections who have received systemic antimicrobials within the 14 days prior to Screening.

4.2.2.2 Inclusion and Exclusion Criteria for Pediatric Stage 2

4.2.2.2.1 Inclusion and Exclusion Criteria for Pediatric Stage 2 Newly Recruited Participants

4.2.2.2.1.1 Inclusion Criteria for Pediatric Stage 2 Newly Recruited Participants

Individuals who meet all of the following criteria are eligible for enrollment as participants in Pediatric Stage 2:

1. Individuals 2-17 years of age that meet classification criteria for SLE, JIA, POMS, or JDM. Note: Juvenile idiopathic arthritis includes the following conditions: polyarticular JIA (both RF + and -), oligoarticular persistent and oligoarticular extended JIA, psoriatic arthritis, and enthesitis related JIA.
 - a. Participants must meet the 2017 EULAR/ACR classification criteria for adult and juvenile idiopathic inflammatory myopathies and their major subgroups [8], the International League of Associations for Rheumatology (ILAR) classification for JIA [4], the 2017 McDonald [6] criteria for MS, or the Bohan and Peter criteria or the 2017 EULAR/ACR classification criteria for JDM.
 - b. If a participant has been diagnosed with more than one autoimmune disease, the participant will be assessed based on the disease that is selected for study entry.
2. Parents/guardians of all pediatric participants and participants ages 14 – 17 must be willing and able to sign informed consent. Participants ages 7-13 must be willing and able to sign assent.
3. Documented full COVID-19 vaccination (CDC card or documentation in medical records).
4. Received an additional COVID-19 vaccine dose (documented by CDC card or in medical records) that was completed at least 4 weeks prior and no more than 48 weeks prior to the Stage 2 Screening visit.
5. Negative or suboptimal serologic response to homologous doses of COVID-19 vaccine in one of the qualifying regimens, defined as an Elecsys® Anti-SARS-CoV-2 S (RBD) negative result or positive result of ≤200 U/mL, or a low immune response, defined as an Elecsys® Anti-SARS-CoV-2 S (RBD) result of ≤2500 U/mL, within 4 weeks of the Stage 2 Baseline/Week 0 visit.

The regimens of COVID-19 vaccination that qualify are as follows:

- a. Pfizer-BioNTech COVID-19 Vaccine (2 through 5 years of age): 4 full, age-appropriate doses of the Pfizer-BioNTech COVID-19 Vaccine
- b. Pfizer-BioNTech COVID-19 Vaccine (5 through 17 years old): 3 full, age-appropriate doses of the Pfizer-BioNTech COVID-19 Vaccine

Note: Participants who are 5 years old and previously received the Pfizer-BioNTech COVID-19 Vaccine may have received either age-appropriate regimen. See Section 3.1.2.2, Pediatric Stage 2 for additional details.

- c. Moderna COVID-19 Vaccine (12 through 17 years of age): 3 full, age-appropriate doses of the Moderna COVID-19 Vaccine
6. Must be currently taking one of the following IS medications with or without additional disease-related medications: MMF (minimum of 250 mg per day)/MPA (minimum of 360 mg per day), MTX (minimum of 5 mg

per week), or B cell depleting agents within the past 18 months (such as rituximab, ocrelizumab, or ofatumumab).

- a. If taking MMF/MPA or MTX, the participant must have initiated therapy at least 8 weeks prior to allocation and be taking the same medications (regardless of dose) as at the time of the initial COVID-19 vaccine regimen. Note: Participants who withheld their IS medications around their initial vaccinations are eligible to participate.
- b. If enrolling in the B cell depleting therapy cohort, participant must have received an anti-CD20 or an anti-CD19 B cell depleting therapy in the past 18 months.

7. No changes in background IS medications, including MMF/MPA or MTX, in the 4 weeks prior to Screening, excluding the following:

- a. HCQ,
- b. Intraarticular steroids,
- c. The addition of prednisone at <0.15mg/kg/dose per day or prednisone at any dose when given for ≤3 days, and
- d. Corticosteroid bursts for non-autoimmune disease-related conditions, such as asthma or COPD, are permitted.

4.2.2.2.1.2 *Exclusion Criteria for Pediatric Stage 2 Newly Recruited Participants*

Individuals who meet any of these criteria are not eligible for enrollment as participants in Pediatric Stage 2:

1. Inability or unwillingness of a participant to give assent or consent; or of a parent/guardian to give written informed consent, or of either to comply with study protocol.
2. History of severe allergic reaction to the initial COVID-19 vaccine regimen, or any component of any of the COVID-19 vaccine, that is to be administered in Stage 2, or to PEG.
3. New diagnosis of malignancy that will require chemotherapy or immunotherapy, or ongoing treatment for a malignancy with chemotherapy or immunotherapy.
4. Active disease (per the Investigator's decision) resulting in inability to hold the IS therapy in the MMF/MPA or MTX arms of the study.
 - a. The potential impact of temporarily holding medication for participants with a recent mild disease flare within 4 weeks should be carefully considered.
5. Active disease during the Screening period resulting in:
 - a. an increase/addition of any IS medications, or
 - b. a suggestion of MS relapse per the investigator
6. Recent or current SARS-CoV-2 infection defined as:
 - a. Documented SARS-CoV-2 infection in the past 30 days (from the day the participant is diagnosed by positive test to Screening).
 - b. Positive result on a molecular COVID-19 test at Screening.
7. Receipt of an additional heterologous COVID-19 vaccine dose prior to Stage 2 Screening, i.e., a participant cannot have received a mixture of mRNA vaccines.
8. Inflammatory myocarditis/pericarditis within 6 weeks of any COVID-19 vaccine doses.
9. Participants with active, ongoing chronic infections.

Note: Participants are permitted to be on chronic prophylactic antimicrobial therapy.

10. Participants with common variable immunodeficiency disease, as well as any participants currently receiving immune globulin replacement therapy.

Note: Participants on IVIG therapeutically may enter the study provided they have sufficiently quiet disease that they can withhold their IVIG from 8 weeks prior to the Screening visit through 4 weeks after vaccination.
11. Participants who received licensed or investigational monoclonal antibodies or plasma products directed against SARS-CoV-2 within 30 days of Screening.
12. Participants who have received any live vaccines within 2 months of the anticipated study vaccine dose or who will have need of a live vaccine at any time during the study.
13. Currently pregnant or breastfeeding (postmenarchal females must have a negative urine pregnancy test at Screening)
14. Hemoglobin (Hgb) <8.0 g/dL (80 g/L)
15. Past or current medical problems or findings from physical examination or laboratory testing that are not listed above, which, in the opinion of the investigator, may pose additional risks from participation in the study, may interfere with the participant's ability to comply with study requirements or that may impact the quality or interpretation of the data obtained from the study.
16. Other investigational chemical agent within 30 days or other investigational biologic agent within 8 weeks or 5 half-lives (whichever is longer) of Screening.
17. Concurrent treatment with cyclophosphamide.
18. Participants currently on any type of dialysis, or who have received a solid organ transplant.
19. Prisoners or participants who are compulsorily detained (involuntarily incarcerated) for treatment of either a psychiatric or physical (e.g., infectious disease) illness must not be allowed to participate in this study.
20. Taking both MMF/MPA and MTX.
21. Other investigational B cell depleting therapy as part of a clinical trial within 18 months of Screening, unless drug assignment is known and the participant received an anti-CD20 or CD19 drug.
22. Participants with active systemic infections who have received systemic antimicrobials within the 14 days prior to Screening.

4.2.2.2.2 Inclusion and Exclusion Criteria for Pediatric Stage 2 Rollover Participants

Individuals who were previously enrolled in Pediatric Stage 1 will have met some inclusion and exclusion criteria at that time. Only a subset of the criteria for entering Pediatric Stage 2 will be assessed in rollover participants at the time of screening for Stage 2. The criteria below are numbered to match the criteria for newly recruited participants. The criteria that are not noted below do not need to be reassessed for rollover participants.

4.2.2.2.2.1 Inclusion Criteria for Pediatric Stage 2 Rollover Participants

Individuals who meet all of the following criteria are eligible to continue as participants in Pediatric Stage 2:

4. Received an additional COVID-19 vaccine dose that was completed at least 4 weeks prior and no more than 48 weeks prior to the Stage 2 vaccination.
5. Negative or suboptimal serologic response to a previous COVID-19 vaccine administration in one of the qualifying regimens, defined as an Elecsys® Anti-SARS-CoV-2 S (RBD) negative result or positive result of ≤200 U/mL, or a low immune response, defined as an Elecsys® Anti-SARS-CoV-2 S (RBD) result of ≤2500 U/mL, within 4 weeks of the Stage 2 Baseline/Week 0 visit.

The regimens of COVID-19 vaccination that qualify are as follows:

- a. Pfizer-BioNTech COVID-19 Vaccine (2 through 5 years of age): 4 full, age-appropriate doses of the Pfizer-BioNTech COVID-19 Vaccine
- b. Pfizer-BioNTech COVID-19 Vaccine (5 through 17 years old): 3 full, age-appropriate doses of the Pfizer-BioNTech COVID-19 Vaccine

Note: Participants who are 5 years old and previously received the Pfizer-BioNTech COVID-19 Vaccine may have received either age-appropriate regimen. See Section 3.1.2.2, Pediatric Stage 2 for additional details.

- c. Moderna COVID-19 Vaccine (12 through 17 years of age): 3 full, age-appropriate doses of the Moderna COVID-19 Vaccine

6. Must be currently taking one of the following IS medications with or without additional disease-related medications: MMF (minimum of 250 mg per day)/MPA (minimum of 360 mg per day), MTX (minimum of 5 mg per week), or B cell depleting agents within the past 18 months (such as rituximab, ocrelizumab, or ofatumumab).
 - a. If taking MMF/MPA or MTX, the participant must have initiated therapy at least 8 weeks prior to allocation and be taking the same medications (regardless of dose) as at the time of the initial COVID-19 vaccine regimen. Note: Participants who withheld their IS medications around their initial vaccinations are eligible to participate.
 - b. If enrolling in the B cell depleting therapy cohort, participant must have received an anti-CD20 or an anti-CD19 B cell depleting therapy in the past 18 months.
7. No changes in background IS medications, including MMF/MPA or MTX, in the 4 weeks prior to Stage 2 Baseline/Week 0, excluding the following:
 - a. HCQ,
 - b. Intraarticular steroids,
 - c. The addition of prednisone at <0.15mg/kg/dose per day or prednisone at any dose when given for ≤3 days, and
 - d. Corticosteroid bursts for non-autoimmune disease-related conditions, such as asthma or COPD, are permitted.

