 - c. Hepatitis C as indicated by anti-hepatitis C antibody positivity; if a participant is Hepatitis C antibody positive, they will be eligible to participate in the study if he/she is negative for viral load at Stage 2 Screening.

Note: Participants are permitted to be on chronic prophylactic antimicrobial therapy.

- 10. Participants with common variable immunodeficiency disease, as well as any participants currently receiving immune globulin replacement therapy.
- 11. Participants who received licensed or investigational monoclonal antibodies or plasma products directed against SARS-CoV-2 within 30 days of Stage 2 Screening.
- 12. Participants who have received any live vaccines within 2 months of the anticipated study vaccine dose or who will have need of a live vaccine at any time during the study.
- 13. Currently pregnant or breastfeeding.
- 14. Female participants who are planning a pregnancy during the course of the trial.
- 15. Hemoglobin (Hgb) <8.0 g/dL (80 g/L)
- 16. Past or current medical problems or findings from physical examination or laboratory testing that are not listed above, which, in the opinion of the investigator, may pose additional risks from participation in the study, may interfere with the participant's ability to comply with study requirements or that may impact the quality or interpretation of the data obtained from the study.
- 17. Other investigational chemical agent within 30 days or other investigational biologic agent within 8 weeks or 5 half-lives (whichever is longer) of Stage 2 Screening.
- 18. Concurrent treatment with cyclophosphamide, cladribine, alemtuzumab, or mitoxantrone.
- 19. Participants currently on any type of dialysis, or who have received a solid organ transplant.
- 20. Prisoners or participants who are compulsorily detained (involuntarily incarcerated) for treatment of either a psychiatric or physical (e.g., infectious disease) illness.
- 21. Taking both MMF/MPA and MTX.
- 22. Receiving other investigational BCDT as part of a clinical trial within 18 months of Stage 2 Screening, unless drug assignment is known and the participant received an anti-CD20 or CD19 drug.
- 23. Participants with active systemic infections who have received systemic antimicrobials within the 14 days prior to Stage 2 Screening.

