4.2.2.2.2 Exclusion Criteria for Pediatric Stage 2 Rollover Participants

Individuals who meet any of these criteria are not eligible to enter Pediatric Stage 2:

2. History of severe allergic reaction to the initial COVID-19 vaccine regimen, or any component of any of the COVID-19 vaccine, that is to be administered in Stage 2, or to PEG.
3. New diagnosis of malignancy that will require chemotherapy or immunotherapy, or ongoing treatment for a malignancy with chemotherapy or immunotherapy.
4. Active disease (per the Investigator's decision) resulting in inability to hold the IS therapy in the MMF/MPA or MTX arms of the study.
 - a. The potential impact of temporarily holding medication for participants with a recent mild disease flare within 4 weeks should be carefully considered.
5. Active disease during the Stage 2 Screening period resulting in:
 - a. an increase/addition of any IS medications, or
 - b. a suggestion of MS relapse per the investigator
6. Recent or current SARS-CoV-2 infection defined as:

- a. Documented SARS-CoV-2 infection in the past 30 days (from the day the participant is diagnosed by positive test to Stage 2 Screening).
- b. Positive result on a molecular COVID-19 test at Stage 2 Screening or Stage 2 Baseline/Week 0.
- 8. Inflammatory myocarditis/pericarditis within 6 weeks of any COVID-19 vaccine doses.
- 11. Participants who received licensed or investigational monoclonal antibodies or plasma products directed against SARS-CoV-2 within 30 days of Stage 2 Screening.
- 13. Currently pregnant or breastfeeding (postmenarchal females must have a negative urine pregnancy test at Screening)
- 14. Hemoglobin (Hgb) <8.0 g/dL (80 g/L)
- 15. Past or current medical problems or findings from physical examination or laboratory testing that are not listed above, which, in the opinion of the investigator, may pose additional risks from participation in the study, may interfere with the participant's ability to comply with study requirements or that may impact the quality or interpretation of the data obtained from the study.
- 16. Other investigational chemical agent within 30 days or other investigational biologic agent within 8 weeks or 5 half-lives (whichever is longer) of Stage 2 Screening.
- 17. Concurrent treatment with cyclophosphamide.
- 18. Participants currently on any type of dialysis, or who have received a solid organ transplant.

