7.3 Prohibited Medications

All participants are to have access to any care deemed medically necessary, but administering the following medications, for the purposes of this study, are prohibited and will be considered protocol deviations unless otherwise noted.

- Any SARS-CoV-2 vaccine administered outside of the study is prohibited.
- All other vaccines administered outside of the study are prohibited between Screening and Week 4 during Stage 1 participation and between Screening and Week 4 during Stage 2 participation.
- Other vaccines, including the flu vaccine, administered within 4 weeks prior to a study visit, starting with the Baseline visit.
- Intravenous or subcutaneously administered immune globulin within 4 weeks prior to a study visit
- Monoclonal antibodies for pre-exposure prophylaxis are prohibited between Screening and Week 4 during Stage 1 participation and between Screening and Week 4 during Stage 2 participation.

If a participant takes a prohibited medication during the study, it should be recorded as a protocol deviation in the eCRF. Participants who received a SARS-CoV-2 vaccine outside of the study will be withdrawn. All other participants will continue to be followed for safety.

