13.4.2 Primary Analysis of Primary Endpoint

The primary endpoint of a protective antibody response will be the proportion of participants who reach the laboratory-defined threshold for the NIAID-VRC MSD 3 plex (Wu-1 full-length spike, RBD, and N proteins) assay. Participants with missing Week 4 anti-COVID-19 antibody response data with a documented COVID infection will be considered as not having a protective antibody response. All other participants missing Week 4 anti-COVID-19 antibody response data will be considered to be missing-completely-at-random (MCAR). Intercurrent events which result in Week 4 anti-COVID-19 antibody response data being unevaluable for immune response, including receipt of monoclonal antibodies or plasma products directed against SARS-CoV-2 and any SARS-CoV-2 vaccine outside of the study, will also result in data being considered to be missing-completely-at-random (MCAR).

The primary analysis will be evaluated independently within each arm (defined by age, cohort, vaccine, and IS treatment plan) and within subgroups with either a negative or suboptimal response to prior vaccines (defined as Roche Elecsys® Anti-SARS-CoV-2 S result \leq 200 U/mL) or with a low immune response (defined as Roche Elecsys® Anti-SARS-CoV-2 S result $>$ 200 U/mL and \leq 2500 U/mL). The primary analysis will be performed in the vaccinated population. The proportion of participants meeting a protective antibody response criteria will be reported in each arm and subgroup with 90% Clopper-Pearson confidence intervals and analyzed using a one-sided exact test with alpha = 0.05 against the null hypothesis that the probability of achieving a protective immune response is \leq 0.25. P-values will not be adjusted for

multiple comparisons. The primary analysis will also be conducted in the subgroup of participants with a Roche Elecsys® Anti-SARS-CoV-2 S result ≤ 50 U/mL at the Screening visit. Each analysis will occur after the evaluable participants assigned to that arm have completed the Week 4 study visit or are withdrawn from the study.

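### Stage 2 rollover lists omit the immune-globulin exclusion that new recruits must meet, and no explicit rule removes an affected Week 4 result from the main analysis

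*Protocol*

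**What the plan says.** **Entry.** Protocol 4.2.1.2.2 (adult) and 4.2.2.2.2 (pediatric) list the criteria checked again at rollover, keep the numbering used for new recruits, and state: "The criteria that are not noted below do not need to be reassessed for rollover participants". Number 10 is absent from both rollover exclusion lists and from the matching lists in the Protocol Synopsis.

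For newly recruited adults (4.2.1.2.1), Exclusion 10 reads: "Participants with common variable immunodeficiency disease, as well as any participants currently receiving immune globulin replacement therapy". The pediatric new-recruit version (4.2.2.2.1) has the same wording plus a note. A child on therapeutic IVIG may enter only if the disease is quiet enough to "withhold their IVIG from 8 weeks prior to the Screening visit through 4 weeks after vaccination".

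Two related exclusions are kept for rollovers. Exclusion 11 covers "Participants who received licensed or investigational monoclonal antibodies or plasma products directed against SARS-CoV-2 within 30 days of Stage 2 Screening". An investigator-judgement exclusion (adult 16, pediatric 15) covers medical problems or findings that, among other things, "may impact the quality or interpretation of the data obtained from the study".

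**Conduct.** Protocol 7.3 lists as prohibited "Intravenous or subcutaneously administered immune globulin within 4 weeks prior to a study visit". It adds: "If a participant takes a prohibited medication during the study, it should be recorded as a protocol deviation in the eCRF". Withdrawal is ordered only for a SARS-CoV-2 vaccine given outside the study.

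**Analysis.** Protocol 13.4.2 uses the vaccinated population. It treats a Week 4 result as missing completely at random when an intercurrent event makes it unevaluable, "including receipt of monoclonal antibodies or plasma products directed against SARS-CoV-2" and outside SARS-CoV-2 vaccines. Protocol 13.4.4 repeats the primary analysis plan for Stage 2. SAP 8.2.1 covers missing Week 4 data and has no rule for intercurrent events.

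**The concern.** Immune-globulin treatment is a state that can change between stages. The pediatric note expects this: withholding ends 4 weeks after vaccination, so a Stage 1 child may resume IVIG before rolling over. An adult may begin replacement therapy after Stage 1 entry. Rollover Inclusion 4 allows up to 48 weeks between the previous dose and the Stage 2 dose. The protocol does recheck other changeable states at rollover, such as monoclonal antibodies, pregnancy and investigational agents, so permanence does not explain leaving out number 10.

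Two things are at stake. Rollovers and new recruits in one arm enter under different immune-globulin rules. And if donor antibody raises the Week 4 Wu-1 spike value over the threshold, a participant counts as a vaccine responder without having responded. A rise before screening could also move someone across the 200 U/mL Elecsys boundary that defines the capped, separately analysed subgroups.

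**Working it through.** **1. What bars entry.** The rollover lists do not include Exclusion 10. Exclusion 11 is limited to products directed against SARS-CoV-2, which ordinary immune globulin is not. The Baseline vaccine-eligibility lists (8.2.4, 8.4.4) address medication changes between Screening or allocation and Baseline. They do not name immune globulin or deal with ongoing use. Only investigator judgement remains.

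**2. How far Section 7.3 reaches.** It covers the 4 weeks before each study visit. The pediatric note starts 8 weeks before Screening, so a dose between 4 and 8 weeks before Screening fails a newly recruited child but need not breach 7.3 for a rollover. After vaccination, a Week 4 visit held a week late leaves the first post-vaccination week outside that visit's window, unless the Week 1 phone contact counts as a study visit. Inside the window, the stated consequence is a recorded deviation.

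**3. What happens to the Week 4 result.** Deviations stay in the vaccinated population (13.4.1). Immune globulin is not named in 13.4.2. The SAP claims primacy where it differs from the protocol (SAP 2) and has no rule in 8.2.1. SAP 6.3 names outside vaccines and monoclonal antibodies for tabulation, not immune globulin.

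**4. Illustration of size.** Inputs from Protocol 13.4.2 and 13.7: null 0.25, alternative 0.5, one-sided exact test at 0.05, 33 evaluable.

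Plan's own figure: the smallest r with P(Bin(33, 0.25) ≥ r) ≤ 0.05 is 13. Exact alpha is 0.0484 and power is P(Bin(33, 0.5) ≥ 13) = 0.919. The stated power of at least 90% reproduces.

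Assumption: k participants count as responders only through donor antibody, and the others respond at 0.25. The documents give no value for k.

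False-positive probability = P(Bin(33 − k, 0.25) ≥ 13 − k). Expected observed proportion = [k + 0.25(33 − k)]/33.

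| k | 33 evaluable, reject at ≥13 | Expected proportion | 40 evaluable, reject at ≥16 |
|---|---|---|---|
| 0 | 0.048 | 0.250 | 0.026 |
| 1 | 0.080 | 0.273 | 0.044 |
| 2 | 0.128 | 0.295 | 0.071 |
| 3 | 0.197 | 0.318 | 0.111 |
| 5 | 0.400 | 0.364 | 0.242 |

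The last column uses the subgroup cap of 40 with nobody missing.

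A softer assumption: a fraction c receive immune globulin, and half of those who would not otherwise respond cross the threshold. The response probability is then 0.25(1 − c) + c(0.25 + 0.75 × 0.5). For c = 5% it is 0.269 and the false-positive probability is 0.080. For c = 10% it is 0.2875 and 0.125.

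**The case against.** The strongest reply is that immune globulin is already substantially guarded. Section 7.3 prohibits it before every study visit. S2 Baseline and Week 4 together cover nearly the whole period from 4 weeks before vaccination to the sample. Concomitant medications are updated at rollover screening (8.2.2.3.2, 8.4.2.3.2), and 8.1.4.1 asks that eligibility assessment include prohibited medications. The investigator-judgement exclusion can be used. Rollovers need an Elecsys result of 2500 U/mL or less within 4 weeks of S2 Baseline, so a large passive rise at screening would block entry. The list in 13.4.2 is open-ended, and the per-protocol repeat (13.4.3, SAP 8.2.3) removes major deviations that affect Week 4.

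Much of this stands. A reader might infer that an immune-globulin user enters Stage 2 with no check at all. The documents do not support that.

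These guards still do not close the gap. The medication review leads back to 7.3, whose breach bars neither entry nor vaccination. An open-ended list leaves the decision to be made after the fact in an open-label trial. The per-protocol analysis is supportive, and use that breaches no stated rule is not a deviation. The Elecsys limit cannot catch a dose given after vaccination. It is arguable whether the SAP's silence is a difference that overrides 13.4.2, but even then 13.4.2 does not name immune globulin.

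A reader might also extend the point to other omitted numbers. That does not hold. Combined MMF/MPA and MTX use is handled for Cohorts D and E by the cohort rules (8.2.2.2, 8.4.2.2). Live vaccines are partly covered by 7.3. Chronic infection has no bearing on passive antibody.

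**Conclusion.** The point holds for Exclusion 10. Rollover participants can enter Stage 2 under a weaker immune-globulin rule than new recruits in the same arm, and the analysis by the primary method has no explicit rule that removes an affected Week 4 result.

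The direction of any bias is upward, provided that immune globulin carries measurable anti-spike antibody. That is an assumption. The documents state neither its antibody content nor how far it moves the assay, and they do not give the protective threshold or the number of users. The rise from 4.8% to 8%, 13% or 20% illustrates one, two or three passive responders among 33, all crossing the threshold. With 40 evaluable the figures are 4.4%, 7.1% and 11.1%. A reader might take these as the trial's actual error rate; the documents do not allow that.

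Nor does the gap in the rollover lists reach the Stage 1 primary objective. The affected result is the Stage 2 response proportion, a secondary objective (2.2.2) in arms without randomisation. The change is worth making because it is cheap and restores one entry rule per arm.

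**What to change.** Reconcile the rollover lists in 4.2.1.2.2, 4.2.2.2.2 and the Synopsis with Exclusion 10 as applied to new recruits, including the pediatric IVIG note, and with Section 7.3, so that one immune-globulin rule governs everyone in an arm. Which withholding period applies is a clinical decision for the sponsor, and none is proposed here.

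In Protocol 13.4.2 and SAP 8.2.1, name immune globulin received within Section 7.3's own prohibited window before the Week 4 sample as an event that makes that result unevaluable, alongside the events already listed.

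The cost is amendment wording and a short SAP addition. The medication data are already collected at rollover screening. The downside is that a few rollovers become ineligible or unevaluable, and each result set to missing draws on the allowance for missing Week 4 data. Starting from 33 evaluable with the rejection rule recalculated, losing one, two or three gives power at 0.5 of 0.892, 0.859 or 0.819, with alpha at or below 0.05. Starting from the cap of 40, it stays above 0.90 (0.946, 0.928, 0.906).
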